Utilizing the PaTH CDRN offers an opportunity to study rural/urban effects, given that the 6 health institution network (University of Pittsburgh Medical Center, Penn State Hershey Medical Center, Temple Health System, Johns Hopkins Health System, University of Utah Health Care, and Geisinger Health System) covers significant populations in both rural and urban counties. For example, PaTH CDRN's service area includes more than 85% of the population of Pennsylvania, including coverage in nearly every one of Pennsylvania's 67 counties (48 rural and 19 urban, see map below). Further, 27% of Pennsylvania's residents live in rural counties, which is higher than the national average of 20%, offering opportunity to better understand diabetes care in this setting. The addition of the University of Utah also offers a different geographic location with similar opportunities to study rural/urban effects. This system provides care for Utahns and residents of five surrounding states in a referral area encompassing more than 10% of the continental US, the vast majority of which is rural. Johns Hopkins Health System, Temple Health System, and the University of Pittsburgh Medical Center offer three different urban populations for comparison.

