**Table 1. Proposed Outcomes for the Pre-diabetes and Diabetes Cohorts**

Outcomes	Definition	Notes
Pre-diabetes cohort		
Weight loss during counseling	Weight lost from first IBT visit to final IBT visit	Available at all PaTH sites
Weight loss maintenance	% of weight lost during program and maintained over remaining time period, reported by year	Available at all PaTH sites
Diabetes incidence	% of patients who develop diabetes per year following weight counseling	Available at all PaTH sites
Patient-reported outcomes	-SF-12 -PHQ-2, PHQ-8, PHQ-9 -Physical function -sleep -fruit and vegetable consumption -social support -physical activity -PROMIS (PROMIS 29, physical function, depression) -healthy lifestyles -patient reported medication reconciliation	Available at some sites – Formal inventory of PROs will be collected at each institution at the beginning of the project, to be included as secondary outcomes
Diabetes cohort		
Weight loss during counseling	Weight lost from first IBT visit to final IBT visit	Available at all PaTH sites
Weight loss maintenance	% of weight lost during program and maintained over remaining time period, reported by year	Available at all PaTH sites
Patient reported outcomes	-SF-12 -PHQ-2, PHQ-8, PHQ-9 -Physical function -sleep -fruit and vegetable consumption -social support -physical activity -PROMIS (PROMIS 29, physical function, depression) -healthy lifestyles -patient reported medication reconciliation	Available at some sites – Formal inventory of PROs will be collected at each institution at the beginning of the project, to be included as secondary outcomes
Uncontrolled diabetes	Average A1c > 9 or no A1c	Available at all PaTH sites
Controlled blood pressure	SBP < 140, DBP < 90, averaged across values over year	Available at all PaTH sites
On a statin medication	Evidence of a statin medication on current EHR medication list	Available at all PaTH sites
Receiving annual eye exam	Documentation of eye exam once in past year	Available at all PaTH sites
Receiving annual urinary microalbumin test	Documentation of lab testing for urinary microalbumin at least once in past year	Available at all PaTH sites
Lower extremity amputations	Documentation of procedure for lower extremity amputation or billing code through health plans in past year	Available at all PaTH sites

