## Analyses of diabetes outcomes at population level

The primary analysis of our study focuses on the individual-level outcomes. The statistical models yield the estimate of average change at individual level post policy implementation. Given the information in the EHR data, we can also aggregate the diabetes outcomes at community level, clinic level, etc. For example, the proportion of patients with controlled diabetes can be obtained for each clinic and used as the outcome variable in the statistical modeling. The proposed mixed-effects modeling framework are still applicable in this case. The statistical analyses can be performed in a similar fashion to that for the individual-level outcomes.

For example, our proposed statistical analysis plan can be easily modified to compare the differences in weight loss and diabetes outcomes (including diabetes control, controlled blood pressure, use of a statin medication, receipt of an annual eye exam and annual urinary microalbumin test, and lower extremity amputations) between rural and urban areas. As stated in the proposal, although our main analysis is on individual-level outcomes, aggregated outcomes at the community- or county-level can also be extracted from the electronic health record (EHR) data. For example, the proportions of patients with controlled diabetes in each county at each year can be obtained and used as the outcome variable after arcsine-square root transformation in the statistical modeling. We can evaluate the rural/urban effects on the pattern of changes in diabetes outcomes over years by including county-level characteristics such as rural vs. urban in the mixed-effects models as fixed effects. The time origin in the analysis will be the beginning of the study period, rather than the time when insurance policy changes occurred. The counties sharing similar characteristics (e.g., access to the same health system) will be considered as a cluster and the clustering effect will be accounted for in the mixed-effects model analysis by including cluster-level random effects. Instead of using segmented regression models to evaluate the trend in diabetes outcomes before and after the policy change, we will consider linear or non-linear trends in the diabetes outcomes and allow rural and urban counties to have different patterns of changes in the models.

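### If the county-level arcsine-square-root form is also used for lower extremity amputations, small rural counties will appear to have fewer amputations than urban ones at equal risk; this is material only at low event rates or thin county coverage

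*Combined protocol and SAP*

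**What the plan says.** Section 8.0, under Analyses of diabetes outcomes at population level, says the plan can be adapted to compare weight loss and a list of diabetes outcomes by rurality. The list ends with "receipt of an annual eye exam and annual urinary microalbumin test, and lower extremity amputations) between rural and urban areas".

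The same paragraph describes a county-level version. Its example is the yearly share of a county's patients whose diabetes is controlled, which is to be "used as the outcome variable after arcsine-square root transformation in the statistical modeling". Rurality enters by "including county-level characteristics such as rural vs. urban in the mixed-effects models as fixed effects", and "the clustering effect will be accounted for in the mixed-effects model analysis by including cluster-level random effects". The section states no weighting by county size, no small-count correction and no separate form for rare outcomes. It also says that the primary analysis is at the individual level.

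Table 1 defines the amputation outcome as "Documentation of procedure for lower extremity amputation or billing code through health plans in past year". That is a yes/no outcome per patient-year, so its county aggregate is a yearly proportion of the kind described.

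Earlier in section 8.0 the plan specifies mixed-effects logistic models for binary outcomes and Poisson models with an offset for counts.

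**The concern.** The function arcsin(√p) is concave below p = 0.5 and very steep near zero. A county-year with no events maps to exactly 0. When the expected count is small, the average transformed value therefore lies below the transform of the true rate, and the shortfall depends on county size. If rural counties hold fewer cohort patients, their transformed means are pulled down further than urban means at the same true risk.

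This is a bias in each county's expected value, not a matter of precision. Size weights or a better variance model change how counties are averaged but leave the bias of each one in place. Section 2.1 justifies the rural focus by poorer rural diabetes care. A transform that lowers the apparent rural amputation rate could mask a rural disadvantage if there is one.

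**Working it through.** The documents give no amputation rate, county patient count or power figure for this analysis, so there is no stated result to reproduce.

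**Inputs from the documents**
- Section 2.1: "67 counties (48 rural and 19 urban, see map below", and "27% of Pennsylvania's residents live in rural counties".
- Section 7.2 table, diabetes patients at the three Pennsylvania sites listed: 25,219 + 150,589 + 40,536 = 216,344.

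**Assumptions**
- All these patients live in Pennsylvania and split by population share.
- Yearly amputation risk is 0.1% to 1%, equal in rural and urban counties.
- Usable patients are all, or a quarter, of the table counts.

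**County sizes**
- Rural: 0.27 × 216,344 / 48 ≈ 1,217.
- Urban: 0.73 × 216,344 / 19 ≈ 8,312, about 6.8 times larger.

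**Method.** For X ~ Binomial(n, p), compute E = Σ P(X = k) · arcsin√(k/n), back-transform as sin²(E), and divide by p. A value of 1 means no bias.

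**Worked case: rural, n = 1,217, p = 0.1%.** The probabilities of 0, 1, 2, 3 and 4 events are 0.296, 0.361, 0.219, 0.089 and 0.027. Their transformed values are 0, 0.0287, 0.0405, 0.0497 and 0.0574. With the small remaining terms, E = 0.0257, against arcsin√0.001 = 0.0316. Then sin²(0.0257)/0.001 ≈ 0.66. The urban county gives 0.97, and the ratio is 0.68.

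**Equal true risk, average county sizes**

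| Rate | Expected events, rural / urban | Back-transformed / true, rural | Same, urban | False ratio, all patients | False ratio, a quarter |
|---|---|---|---|---|---|
| 0.1% | 1.2 / 8.3 | 0.66 | 0.97 | 0.68 | 0.32 |
| 0.3% | 3.7 / 24.9 | 0.91 | 0.99 | 0.92 | 0.60 |
| 0.5% | 6.1 / 41.6 | 0.96 | 0.99 | 0.96 | 0.75 |
| 1% | 12.2 / 83.1 | 0.98 | 1.00 | 0.98 | 0.90 |

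**Threshold.** At n = 1,000, back-transformed over true risk is 0.60 for 1 expected event, 0.81 for 2, 0.94 for 5, 0.97 for 10 and 0.99 for 20. Hence the working limit of about 10.

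**Weighting.** With lognormal county sizes (log-SD 0.7) and all patients, the ratio at 0.1%, 0.3% and 0.5% is 0.60, 0.85 and 0.92 unweighted, and 0.72, 0.91 and 0.96 weighted by n. Weighting reduces the bias but does not remove it.

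**False findings at nominal two-sided 5%.** Two simulations of size-weighted county data over 11 years:
- No true county variation, log-SD 0.7, robust standard errors, 1,500 runs: rural falsely lower in 99.9%, 80% and 52% of runs at 0.1%, 0.3% and 0.5%; never falsely higher.
- 10% true county variation, size CV 0.8, 500 runs: a false difference in 99%, 57% and 11% of runs at 0.1%, 0.3% and 1%.

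The two designs differ, so these percentages show direction and order of size only.

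**Trend.** If every county grows 50% from the sizes above (assumed), the false ratio moves from 0.684 to 0.799 at 0.1%, a drift of 17%. The drift is 3.5% at 0.3%, 1.5% at 0.5% and 0.6% at 1%.

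**The plan's own example.** For true proportions of 0.5 to 0.8 at these county sizes, the back-transformed value is off by less than 0.0002.

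**The case against.** The strongest objection is that the plan never says amputations will be transformed. The arcsine sentence is an example, it names controlled diabetes only, and the wording around it is permissive. The same section says aggregate analyses can follow the individual-level approach, which would mean logistic or Poisson models. A reader might infer that the plan commits to a biased amputation analysis; the text does not support that. What stands is that amputations are listed for this comparison, and the only form shown for a county-year proportion is one that fails for rare events.

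Second, the primary analysis is at the individual level. Table 1 lists rural versus urban among the individual-level exposures, and binary outcomes get a logistic model. That route has no such bias. This stands in full and limits the point to a secondary analysis.

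Third, the county model is aimed mainly at patterns of change over years, and a constant level bias does not enter a trend difference when rates and county sizes are stable. This stands in part: the section also speaks of comparing differences, and both cohorts are dynamic, but the trend drift is appreciable only at the lowest rates.

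Fourth, the size rests on figures the documents lack. Geisinger is absent from the section 7.2 table and could raise rural counts, Maryland and Utah counties are left out, and the visit-or-claims restriction would lower counts. This stands, and is why a range is shown.

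A reader might also infer that a known rural excess of amputations would be reversed. Section 2.1 cites higher rural diabetes prevalence and poorer services, but no such excess.

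**Conclusion.** The concern holds in conditional form. If the arcsine-square-root form is carried over to amputations, the rural/urban level comparison is biased towards fewer rural amputations, with or without size weights. The direction was the same in every scenario run, provided rural counties hold fewer cohort patients. The size depends on the true rate and county coverage: slight at about 0.5% to 1% with all the tabulated patients (ratio 0.96 to 0.98), and large at 0.1% or with a quarter of them (0.32 to 0.75 for rates up to 0.5%). Common outcomes and the primary individual-level analysis are not affected. Severity is minor.

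**What to change.** Add to the population-level section that the arcsine-square-root form is limited to common outcomes. Amputations, and any other outcome with small expected county-year counts (below about 10), should instead be analysed in one of these ways:
- county event counts in a binomial mixed model with logit link;
- county event counts in a Poisson mixed model with the log denominator as offset, the form section 8.0 already gives for count outcomes;
- the individual-level logistic model.

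Report a rural/urban rate ratio or odds ratio.

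A corrected transform is not a clean substitute. At 0.1% with log-SD 0.7 and all patients, the Anscombe version gives a false ratio of 1.27 unweighted and 1.14 weighted, and Freeman-Tukey gives 1.17 and 1.10, which is bias in the opposite direction.

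The cost is a sentence or two in the plan. No new data or new class of model is needed.

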## **9.0 Confidentiality, Privacy and Data Management**

See Data Plan Review Form HRP-598

### **9.1 Confidentiality**

#### **9.1.1 Identifiers associated with data and/or specimens**

- Names;
- All geographical subdivisions smaller than a State, including street address, city, county, precinct, zip code, and their equivalent geocodes;
- Birth date, admission date, discharge date, date of death;
- Phone numbers;
- Fax numbers;
- Electronic mail addresses;
- Social Security numbers;
- Medical record numbers;
- Health plan beneficiary numbers;
- Account numbers;
- Certificate/license numbers;
- Vehicle identifiers and serial numbers, including license plate numbers;
- Device identifiers and serial numbers;
- Web Universal Resource Locators (URLs);
- Internet Protocol (IP) address numbers;
- Biometric identifiers, including finger and voice prints;
- Full face photographic images and any comparable images (including videos);
- Any other unique identifying number, characteristic, or code (note this does not mean the unique code assigned by the investigator to code the data);
- Other (please specify):

##### **9.1.1.1 Use of Codes, Master List**

N/A

#### **9.1.2 Storage of Data for This Study**

N/A

### **9.1.3 Access to Data for This Study**

N/A

### **9.1.4 Transferring Data for This Study**

N/A

## **9.2 Subject Privacy**

N/A

## **10.0 Risks**

Only de-identified patient level data will be collected, so while loss of confidentiality is a risk, it's unlikely. To minimize the likelihood of a breach in confidentiality, we will follow standard PaTH procedures with regards to data management. Individual health data will be de-identified at each institution and loaded into the PaTH i2b2 instance, transferred, and stored at the University of Pittsburgh CERC-DC.

## **11.0 Potential Benefits to Subjects and Others**

### **11.1 Potential Benefits to Subjects**

None

### **11.2 Potential Benefits to Others**

Potential benefits to others include understanding the effectiveness of obesity counseling benefits for patients with type 2 diabetes an at-risk for diabetes.

## **12.0 Other Approvals**

### **12.1 Other Approvals from External Entities**

N/A

### **12.2 Internal PSU Committee Approvals**

#### **Check all that apply:**

- Anatomic Pathology – Hershey only – Research involves the collection of tissues or use of pathologic specimens. Upload a copy of the Use of Human Tissue For Research Form on the Supporting Documents page in CATS IRB. This form is available on the IRB website at:  
<http://www.pennstatehershey.org/web/irb/home/resources/forms>
- Animal Care and Use – All campuses – Human research involves animals and humans or the use of human tissues in animals
- Biosafety – All campuses – Research involves bio-hazardous materials (human biological specimens in a PSU research lab, biological toxins, carcinogens, infectious agents, recombinant viruses or DNA or gene therapy).
- Conflict of Interest Review – All campuses – Research has one or more of study team members indicated as having a financial interest.
- Radiation Safety – Hershey only – Research involves research-related radiation procedures. All research involving radiation procedures (standard of care and/or research-related) must upload the Radiation Review Form on the Supporting Documents page in CATS IRB. This form is available on the IRB website at:  
<http://www.pennstatehershey.org/web/irb/home/resources/forms>
- IND/IDE Audit – All campuses – Research in which the PSU researcher holds the IND or IDE or intends to hold the IND or IDE.
- Scientific Review – Hershey only – All investigator-written research studies requiring review by the convened IRB must provide documentation of scientific review with the IRB submission. The scientific review

requirement may be fulfilled by one of the following: (1) external peer-review process; (2) department/institute scientific review committee; or (3) scientific review by the Clinical Research Center Advisory committee. Note: Review by the Penn State Hershey Cancer Institute Scientific Review Committee is required if the study involves cancer prevention studies or cancer patients, records and/or tissues. For more information about this requirement see the IRB website at:  
<http://www.pennstatehershey.org/web/irb/home/resources/investigator>

## 13.0 Multi-Site Research

### 13.1 Communication Plans

The lead investigative team (Core PI, co-PIs, core project manager) meet on a bi-weekly basis to create and modify the protocol and well as address any issues that arise from any of the sites. The core project manager and core Principal Investigator will work together to create a standard protocol and disseminate it among the sites to submit to each institution's IRB. The core project manager will also coordinate and review any modifications to the protocol with both the lead team and with all the site project managers (there is a project manager for each site) to submit the appropriate changes to their IRB.

### 13.2 Data Submission and Security Plan

To minimize the likelihood of a breach in confidentiality, we will follow standard PaTH procedures with regards to data management. Individual health data will be de-identified and loaded into the PaTH i2b2 instance, transferred, and stored at the University of Pittsburgh CERC-DC. No identifiable patient information will leave institutional firewalls. Data analysis by Penn State investigators will occur through secure remote computing. No patients will be contacted for this study.

### 13.3 Subject Enrollment

The lead investigative team will meet regularly and communicate with the PaTH project manager to coordinate data extraction.

### 13.4 Reporting of Adverse Events and New Information

N/A

### 13.5 Audit and Monitoring Plans

There are several processes in place to ensure all site investigators conduct the study appropriately. First, PaTH has multiple internal procedures to ensure data is accurate. Given the study is reliant on the PaTH Network, a regular meeting schedule will be determined to ensure the data is being extracted and reported to meet study requirements in accordance with protocol. Local procedure will include the Penn State study team (PI, core project manager) jointly overseeing the auditing and monitoring plans. Specifically, the PCORI milestones have been back-dated to allow one month for review by the PI and core project manager. Data will be checked for completeness and accuracy, based on expected values and ranges. Biweekly meetings between the PI and core project manager will be used to review protocol and site progress and ensure proper conduction of the study.

## 14.0 Adverse Event Reporting

### 14.1 Reporting Adverse Reactions and Unanticipated Problems to the Responsible IRB

In accordance with applicable policies of The Pennsylvania State University Institutional Review Board (IRB), the investigator will report, to the IRB, any observed or reported harm (adverse event) experienced by a subject or other individual, which in the opinion of the investigator is determined to be

(1) unexpected; and (2) probably related to the research procedures. Harms (adverse events) will be submitted to the IRB in accordance with the IRB policies and procedures.

## 15.0 Study Monitoring, Auditing and Inspecting

### 15.1 Auditing and Inspecting

The investigator will permit study-related monitoring, audits, and inspections by the Penn State quality assurance program office(s), IRB, the sponsor, and government regulatory bodies, of all study related documents (e.g., source documents, regulatory documents, data collection instruments, study data etc.). The investigator will ensure the capability for inspections of applicable study-related facilities (e.g., pharmacy, diagnostic laboratory, etc.)

## 16.0 Future Undetermined Research: Data Banking

N/A. This study is not collecting or retaining identifiable data.

### 16.1 Data being stored

N/A

### 16.2 Location of storage

N/A

### 16.3 Duration of storage

N/A

### 16.4 Access to data

N/A

### 16.5 Procedures to release data

N/A

### 16.6 Process for returning results

N/A

